Effects of Unloader Bracing in Clinical Outcome and Articular Cartilage Physiology Following Microfracture of Isolated Chondral Defects

Statistical Analysis Plan
NCT02016300

March 28, 2019

The primary endpoints were change in three MRI outcomes at 24 months: T2 relaxation times, repair region volume, and repair region thickness. Secondary endpoints included the KOOS sub-scores, the VR-12 score, the Lysholm score, and the Tegner score. For the primary and secondary endpoints, differences in the groups for T2 relaxation time, repair region volume, and repair region thickness and clinical outcomes were examined using multilevel, repeated measures linear regression models. A Bonferroni correction was used to adjust for multiple comparisons. The adjusted p-value was .008. We aimed to assess whether the data provided evidence of superiority of the off-loading brace in recovery after microfracture surgery.

Subgroup analyses examining correlations between questionnaire items and brace data were conducted with analyses limited to patients in the off-loading brace group. The number of days the brace was worn, the average number of minutes per day that the brace was worn, and the total number of minutes the brace was worn were calculated for patients in the off-loading brace group. Correlations were also examined between either the questionnaire items at each time point or the change from baseline to each time point in relationship to the total number of days the brace was worn or the total number of minutes the brace was worn over all days. Similarly, correlations were assessed between the MRI data at each time point and the change from baseline to each time point and the total amount of time the brace was worn. Data were analyzed using R and Rstudio (R Core Team, 2018; Rstudio Team, 2016). No interim analyses were performed.

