
Clinical outcome will be assessed at MRI follow-up time points using: The **Knee injury and Osteoarthritis Outcome Score (KOOS)** questionnaire is a standard clinical tool used to evaluate short-term and long-term symptoms and function in subjects with knee injury and osteoarthritis. It is broken up into five subcategories: Knee symptoms, knee pain, Function in daily living (ADL), Function in Sport and Recreation (Sport/Rec), and knee-related Quality of Life (QOL). The KOOS is a validated, reliable and responsive self-administered instrument that can be used for short-term and long-term follow-up of osteoarthritis and will be given to our patients to evaluate the effect of the unloading braces. The KOOS incorporates the commonly used WOMAC survey.

Tegner activity level scale will be used to establish standardized activity levels pre and post treatment. **VR-12** quality of Life questionnaire will be used to establish changes in quality of life. **Lysholm** score will be used to reflect symptoms with activities of daily living. **VAS (Visual Analog Scale)** will be used to determine the level of patient pain at each visit.

Schedule of Appointments

Visit 1 (T=0)

Visit 1 will be the baseline visit and will take place at the first post operative visit. Participants will undergo the informed consent process. Once signed, participants will answer standardized questionnaires (see above), get fitted for the brace (if in bracing group), and undergo baseline MRI scans and x-rays to evaluate alignment. Wearing of the brace will commence at the time of weight bearing, which will occur immediately post-operatively in Centre 2 (Japan) and 8 weeks post operatively at Centre 1 (USA).

Brace fitting

Each participant will be fitted by a licensed orthotist for the Unloader brace.

Imaging

Each participant will undergo a pre-study series of X-rays that are standard for osteoarthritis examination. This series consists of a front-view (AP) X-ray of the knees, a sideways (lateral) view, and a one with the knee flexed at 45° (Rosenberg). There will also be a long standing X-ray (36") that will film the lower extremities. These films will measure any mal-alignment present.

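### The SAP holds every comparison to a fixed Bonferroni threshold of .008 without defining the family or alpha; once these are stated, Holm would give the same error control with modestly more power

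*SAP*

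**What the plan says.** The SAP names three primary endpoints: "The primary endpoints were change in three MRI outcomes at 24 months: T2 relaxation times, repair region volume, and repair region thickness". It then lists the secondary ones: "Secondary endpoints included the KOOS sub-scores, the VR-12 score, the Lysholm score, and the Tegner score". The Protocol, under Outcome Measures, says of the KOOS that "It is broken up into five subcategories".

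The modelling sentence covers both tiers together: "For the primary and secondary endpoints, differences in the groups for T2 relaxation time, repair region volume, and repair region thickness and clinical outcomes" are examined with multilevel repeated-measures regression. Straight after it come the two sentences on multiplicity: "A Bonferroni correction was used to adjust for multiple comparisons" and "The adjusted p-value was .008". The stated aim is superiority: "We aimed to assess whether the data provided evidence of superiority of the off-loading brace in recovery after microfracture surgery".

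No step-down rule is mentioned. The SAP gives no number of comparisons, family-wise alpha or sidedness, and does not say how many of the three primaries must succeed. It is dated March 28, 2019 and is written in the past tense.

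**The concern.** A fixed threshold keeps every endpoint at the strictest level even after another member of the family has been rejected. Holm relaxes the threshold after each rejection without raising the family-wise error rate. Suppose the family is three tests at .05 and one primary has p at or below .0167. A second primary with p between .0167 and .025 is then negative under Bonferroni and positive under Holm, on the same data.

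The Protocol describes a 40-patient pilot and gives no sample-size calculation, so power that can be had at no cost in error control is worth having. Holm cannot be applied, however, until the family and its alpha are declared, and the SAP declares neither.

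**Working it through.** **Step 1. Where .008 could come from.** The Bonferroni threshold is alpha/m.

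| Family alpha | m | alpha/m | Rounds to .008? |
|---|---|---|---|
| .05 | 3 (the primaries) | .0167 | no |
| .05 | 6 | .00833 | yes |
| .025 | 3 (the primaries) | .00833 | yes |
| .10 | 12 | .00833 | yes |
| .05 | 11 (3 primaries + 5 KOOS + VR-12 + Lysholm + Tegner) | .0045 | no |

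The plan's figure can be matched in more than one way, and neither alpha nor m is printed. If .008 is used for each test, the alpha spent is 3 × .008 = .024, 6 × .008 = .048 or 11 × .008 = .088, depending on the family.

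**Step 2. The two rules.** Bonferroni rejects each hypothesis with p ≤ alpha/m. Holm orders the p-values, compares them in turn with alpha/m, alpha/(m−1), and so on, and stops at the first failure. The Holm thresholds are:

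- three tests at .05: .0167, .025, .05
- three tests at .025: .0083, .0125, .025
- six tests at .05, first three steps: .0083, .0100, .0125

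The first step is the same as Bonferroni's, so the chance of at least one rejection is identical and the other rejections can only increase.

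**Step 3. Inputs for power.** From the Protocol (Recruitment; Initial post-operative protocol): 20 patients at each of two centres and 10 per group per centre, hence 20 per arm. Assumed, because the documents give no figures: two-sided tests, standardised effects of 0.5 to 0.8 SD, volume-thickness correlation 0.8, correlation of T2 with each 0.3, and no dropout. Two-sample t-tests stand in for the multilevel models.

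**Step 4. Simulated power per endpoint.**

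| Scenario | Family | Bonferroni | Holm |
|---|---|---|---|
| 0.8 SD on all three | .05, m = 3 | 51-52% | 59-60% |
| 0.8 SD on all three | .025, m = 3 | 41% | 47-48% |
| 0.8 SD on all three | .05, m = 6 | 41% | at least 44% |
| 0.5 SD on all three | .05, m = 3 | 19% | 22-23% |
| 0.8 SD on volume and thickness only | .05, m = 3 | about 52% | about 55% |
| 0.8 SD on T2 only | .05, m = 3 | 51.7% | 51.9% |

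The six-test row is a lower bound because the other three tests are taken as not rejected. The last two rows show power for the endpoints that respond. Family-wise error under the global null is about 4.2% for both methods in the .05, m = 3 setting.

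A separate normal-approximation run (T2 correlation 0.2, 0.8 SD on all three, .05, m = 3) gave 55% against 63-64% per endpoint. The chance of at least one rejection was 81.4% under both methods.

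**Step 5. Role of the volume-thickness correlation.** At 0.8 SD on all three (.05, m = 3), Holm's gain for volume and thickness is about 8.5 points at correlation 0.1, 7.5 at 0.8 and 6.5 at 0.95. Global-null error falls from about 4.7% to 3.8% over the same range, equally for both methods.

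**Step 6. Size of the undefined divisor.** In the same 0.8 SD setting, a threshold of .0167 gives 51-52% per endpoint and .0083 gives 41%, about 10 points apart. Which family was meant therefore matters at least as much as the choice of procedure.

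**The case against.** The strongest reply is that Bonferroni is valid, simple and comes with matching simultaneous confidence intervals, so preferring Holm is a matter of efficiency. That stands. The gain is also conditional: it needs real effects on several endpoints, it is small at 0.5 SD, and it nearly vanishes if only T2 responds. Nothing in the SAP requires all three primaries to succeed, so power to show all three together is not its criterion. These points stand too, and they limit the weight of the recommendation.

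Timing is a further objection. The SAP reads as an account of analyses already done, and moving to a more liberal rule once results are known is post hoc. That restricts how Holm may be presented, but it does not restrict reporting it openly beside Bonferroni.

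Two stronger readings are tempting. First, a reader might infer that the correction covers exactly the three primaries at .05. The text does not say so: the preceding sentence takes primary and secondary endpoints together, and .05/3 is .0167. Second, since "T2 relaxation times, repair region volume, and repair region thickness" include two measures of the same repair region, a reader might infer that this overlap makes Bonferroni especially wasteful and Holm especially helpful. The documents give no correlation between volume and thickness. Holm does not use correlation in any case, and Step 5 shows its gain for these two endpoints shrinking as their correlation rises. Recovering the conservatism due to overlap would need a method based on the joint distribution.

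**Conclusion.** The point holds as a modest efficiency improvement that depends on first defining the family. At 0.8 SD on all three primaries, Holm adds about 8 points of power per endpoint for three tests at .05, 6 to 7 for three tests at .025, and at least 3 for six tests at .05. At 0.5 SD (three tests at .05) it adds 3 to 4 points. It never lowers power and leaves the chance of at least one rejection unchanged.

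All these sizes rest on the assumed effects and correlations, 20 per arm with no dropout, and t-tests in place of the planned models. The algebraic properties of Holm do not depend on them. The documents do not support calling the Bonferroni correction an error. The missing definition of the family behind .008 is the more consequential gap in these sentences.

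**What to change.** 1. State the number of comparisons, which endpoints and visits they cover, the family-wise alpha and the sidedness, so that .008 can be derived. Call it a per-comparison significance threshold, not an adjusted p-value.
2. Replace the fixed threshold with Holm across that declared family and report Holm-adjusted p-values. Bonferroni intervals can still be shown, since intervals that match Holm are less simple.
3. If results were already known when the change is made, label the Holm analysis post hoc and give the Bonferroni result alongside.

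The cost is a few SAP sentences. Holm adjustment is in base R, which the SAP already uses, and works from the raw p-values with no new data. The only statistical cost is the less convenient matching intervals.

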A pilot study will be carried out at two centers. 20 patients will be enrolled at each center and be randomized to 2 groups. Patients will be identified from preoperative clinical and radiographic evaluation as potential candidates for the study, however as eligibility will depend on arthroscopic assessment of the cartilage lesion at the time of surgery final enrollment will occur immediately post operatively.

Inclusion criteria include a discrete, contained chondral defect less than 2cm² in size located on the medial or lateral femoral condyle, age between 18-40 years, and overall neutral lower limb mechanical alignment (<5 degrees varus or valgus). Exclusion criteria include previous chondral procedures, osteoarthritis (Kellgren-Lawrence Grade ≥ 2), or significant concomitant knee pathology such as a meniscal tear requiring treatment or a ligamentous instability. Patients who have previously undergone ACL reconstruction or meniscal repair will still be eligible for inclusion in the study.

Initial post-operative protocol

All patients will participate in physical therapy two times per week, use a continuous passive motion device for eight weeks and will have no ROM restrictions. Following enrollment, 10 patients will be randomized into one of two groups at each center. Group 1 will be fitted with the Ossur Unloader One brace. Group 2 will be treated without a brace. At Center 1 (USA), patients will be initially kept non-weight bearing for a period of 8 weeks prior to applying an unloader brace. At Centre 2 (Japan), patients will wear an off-loading brace and commence weight bearing immediately post-operatively. Non-bracing group will be NWB for 8 weeks at both centers.

Outcome Measures

Radiographic outcome will be assessed using baseline, 6 month, and one and two year MRI scans which will assess the quality of the cartilage repair. T1 Rho and T2 mapping will be used to assess regenerate cartilage composition compared to surrounding normal cartilage, surface integrity, average cartilage thickness and the percentage to which the defect is filled. MRI mapping protocols investigate cartilage health by looking at glycosaminoglycan (GAG) concentration. Higher concentrations of GAG generally indicate healthier cartilage. Moreover, correlations have been found between T2 values and cartilage hydration, collagen fiber orientation, and loss of type 2 collagen, suggesting some degree of specificity for targeting the spatial collagen architecture of the matrix.⁶

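### The brace-wear correlations use raw levels and raw change scores with no baseline covariate, so if wear is related to baseline at least one of each pair is biased even when wear has no effect

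*SAP*

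**What the plan says.** The second paragraph of the SAP describes the wear analyses. "Subgroup analyses examining correlations between questionnaire items and brace data were conducted", with "analyses limited to patients in the off-loading brace group". The exposure is "the total number of days the brace was worn or the total number of minutes the brace was worn over all days". The outcome is "either the questionnaire items at each time point or the change from baseline to each time point". For imaging, "correlations were assessed between the MRI data at each time point and the change from baseline to each time point", again against total wear time.

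The SAP names only correlations here. It states no baseline covariate, partial correlation, regression or centre term, and no rule for what to conclude if the level and change results disagree. The multilevel models in its first paragraph are described for differences between the groups only. Baseline therefore enters the wear analyses only by subtraction. The text is silent on adjustment; it does not rule it out.

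The protocol (Recruitment) says that "20 patients will be enrolled at each center and be randomized to 2 groups", and under Initial post-operative protocol that "10 patients will be randomized into one of two groups at each center". That is at most 2 × 10 = 20 braced patients. Questionnaires and MRI are taken at Visit 1, the visit at which the brace is fitted, and wear is then recorded for six months (Brace wear and documentation). The protocol itself plans no analysis of wear against outcome; it only compares sensor wear with the diaries.

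**The concern.** How long a patient wears the brace is decided after randomisation and may depend on the state of the knee at the start. A follow-up level carries the baseline forward. A change score usually carries it with the opposite sign, through regression to the mean. A simple correlation of wear with either one can therefore reflect who chose to wear the brace and not what the brace did.

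This would remain true of a single correlation with complete wear data from one centre, so it is separate from the number of correlations run. What is at stake is the only planned analysis that links amount of wear to outcome. In a small pilot, a false dose-response in either direction could be taken as evidence for or against the brace.

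**Working it through.** The documents give no correlation, power or sample-size figure for these analyses, so there is no figure to reproduce. The check asks what the planned correlations show when wear does nothing.

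**Inputs from the documents**
- Braced patients: n = 20 at most (protocol, Initial post-operative protocol).
- Threshold: .008 is the only one in the SAP. Whether it covers the wear correlations is not stated, so .05 and .008 are both shown, two-sided by assumption.

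**Assumed inputs (not in the documents)**
- b = corr(wear, baseline)
- r = corr(baseline, follow-up)
- s = SD at follow-up / SD at baseline

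**Formulas, with wear related to follow-up only through baseline**
- corr(wear, level) = r·b
- corr(wear, change) = b·(r·s − 1) / √(1 + s² − 2·r·s)
- With s = 1 the second reduces to −b·√((1 − r)/2).

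Take b ≠ 0. The first is zero only if r = 0. The second is zero only if r·s = 1, which needs r ≠ 0. Both cannot hold, so at least one correlation is biased. The expected signs are opposite when 0 < r·s < 1, which is guaranteed by equal SDs with 0 < r < 1.

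**Expected values**
- b = r = 0.5, s = 1: level 0.5 × 0.5 = +0.25; change −0.5 × √0.25 = −0.25.
- b = 0.5, r = 0.3, s = 1: +0.15 and −0.30.
- b = 0.5, r = 0.7, s = 1: +0.35 and −0.19.
- b = r = 0.5, s = 2: +0.25 and 0, because r·s = 1.
- b = r = 0.5, s = 3: +0.25 and 0.5 × 0.5/√7 = +0.09, the same sign.

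**False-positive rates by simulation** (n = 20, s = 1, Pearson tests, no wear effect; at .05 the critical |correlation| is 0.444)

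| b | r | Level, .05 | Change, .05 | At least one, .05 | At least one, .008 |
|---|---|---|---|---|---|
| 0 | 0.5 | 5% | 5% | 9% | 1.5% |
| 0.3 | 0.5 | 10% | 9–10% | 18–19% | 4% |
| 0.5 | 0.3 | 10% | 25% | 34% | 10% |
| 0.5 | 0.5 | 19% | 19% | 36–37% | 10% |
| 0.5 | 0.7 | 34% | 13% | 44% | 15% |

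At r = 0.5, the at-least-one figure at .05 is about 13% for b = 0.2 and about 10% for b = 0.1. At b = r = 0.5 each single test rejects in about 5% of trials at .008. The two estimates then have opposite signs in 73% of trials, against 33% with b = 0, but both are significant with opposite signs in under 1%.

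**After adjustment.** The partial correlation of wear with follow-up given baseline averages about zero in the same settings. It rejects in about 5% of trials at .05 and 0.7–0.8% at .008.

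**Limits of adjustment**
- *Wear that reacts to later symptoms.* With b = 0 and an assumed correlation of 0.3 between wear and the part of follow-up not explained by baseline, the partial correlation rejects in 24% at .05, against about 20% for each raw version.
- *Baseline measured with error.* With error-free correlations of 0.5 (wear-baseline) and 0.6 (baseline-follow-up) and reliability 0.7 to 0.9, all assumed, a partial correlation of 0.04 to 0.09 remains. The raw values are +0.25 to +0.29 (level) and −0.16 to −0.20 (change).

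**The case against.** The premise is conditional. Nothing in the documents shows that wear depends on baseline, and with a weak link the excess is small: about 10% for the pair at b = 0.1, against 9% with no link. If the planned time points include baseline, the SAP's own set already contains the correlation that would reveal the problem. The documents do show another determinant of total wear, namely that the brace starts immediately at Centre 2 and at 8 weeks at Centre 1. These are also subgroup correlations in a pilot. All of this stands. It limits the size of the concern but does not supply the missing covariate.

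A reader might infer that level and change correlations must always point in opposite directions. They need not. Opposite signs are an expectation that requires 0 < r·s < 1, and the documents give neither SDs nor correlations. Baseline is taken soon after surgery, so its spread could be restricted, which would make s exceed 1.

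A reader might also infer that the trial is likely to report two contradictory significant findings. At b = r = 0.5 that happens in under 1% of trials. The more realistic harm is one false finding.

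Finally, one might infer that adjusting for baseline makes the wear result causal. It does not. Wear that reacts to later symptoms and centre differences in brace start both remain.

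**Conclusion.** The concern holds as a conditional one. The SAP correlates non-randomised wear with raw levels and raw changes and states no baseline covariate. If wear is related to baseline, at least one of each pair of correlations is biased when wear has no effect, and running both gives no protection.

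The headline size, 36–37% for at least one false positive per pair against 9%, rests on four assumptions: n = 20, b = 0.5, r = 0.5 and equal SDs. If .008 applies, the comparison is 10% against 1.5%. Fewer braced patients or a weaker link give smaller figures. The remedy is cheap and removes this particular bias, apart from a small residual due to measurement error, so the change should be made. It does not bear on the validity of the randomised comparison.

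**What to change.** - Make the main wear analysis, for each outcome and time point, the regression slope of the follow-up value on wear with its 95% CI (or the partial correlation), adjusted for that outcome's Visit 1 value.
- Report corr(wear, baseline) for each outcome, so that readers can see whether the problem arises.
- If the raw level and change correlations are kept, label them descriptive.
- State that the wear results are observational: adjustment does not remove wear that reacts to later symptoms or centre differences in brace start, and it leaves some bias if baseline is measured with error.

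The cost is one degree of freedom (17 instead of 18 at n = 20) and a change of SAP wording. Because the SAP describes these analyses as already done, it also means re-running a subgroup analysis. No new data are needed, since the protocol already collects the Visit 1 questionnaires and MRI.

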A MRI scan during the first visit will examine cartilage physiology. The scans will take place at the Stanford Medical Outpatient Center or Stanford Medical Lucas Imaging Center with a 3T scanner. Subjects will undergo 2D-T2 mapping, 3D-T2 mapping, and 3D-T1rho mapping. These scans take approximately 12, 10, and 6 minutes, respectively. The total time for the first visit will last approximately 2 hours.

Brace wear and documentation

All patients will be provided with a hard copy bracing diary for the 6-month study duration. Patients will be instructed to document the number of hours for which they wear the brace each day. Diaries will be collected at Visit 2 and daily and weekly averages will be calculated for all patients.

Each Unloader brace will be equipped with an iButton temperature sensor that acquires temperature readings every 20 minutes to objectively document brace wear. The temperature threshold to determine brace wear is set at 25C. The iButton captures and stores these measurements for 1 month after which it must be reprogrammed; all participants will therefore undergo five iButton swaps. These visits will be managed by the orthotist who performs the initial brace fitting. The final iButton will be obtained at Visit 2. iButton data files will be post-processed by [name] and daily and weekly averages calculated for each participant. These values will be compared with the bracing diaries completed by each patient.

Visit 2 (T=6 Months)

Visit two will consist of quantitative MRI scans conducted at the Stanford Medical Outpatient Center or the Stanford Lucas Imaging Center. The patient will also complete the same standardized questionnaires as in the first visit.

Visit 3 (T= 12 months)

The patient will return for another quantitative MRI scan and to answer the standardized questionnaires.

Visit 4 (T= 24 months)

The patient will come back again for a final MRI mapping scan and to answer the standardized questionnaires.

Benefits

All subjects requiring bracing will receive a fitted Unloader One off the shelf brace as compensation for their participation in the study.

Budget

Standard treatment costs, which the study sponsor will NOT be responsible for, include:

1. office visits

2. standard x-ray series
3. off-loader bracing (insurance reimbursement portion)

Sponsor study costs (per study site):

Year 1:

1. Any patient costs for Unloader brace NOT covered by insurance (unknown)

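### If both centres contribute data, correlating total brace wear with outcome without a centre term can turn a centre or regimen difference into an apparent wear effect, or hide a real one

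*SAP*

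**What the plan says.** The second paragraph of the SAP restricts the brace-wear analyses to patients in the off-loading brace group. Three wear summaries are calculated: days worn, average minutes per day, and total minutes. The questionnaire correlations, both at each time point and as change from baseline, are with the "total number of days the brace was worn or the total number of minutes the brace was worn over all days". The MRI correlations use the total time worn. No centre covariate, stratum or scaling to the available wear period is given, and the SAP never mentions centres.

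The protocol (Initial post-operative protocol) sets different starts: "At Center 1 (USA), patients will be initially kept non-weight bearing for a period of 8 weeks prior to applying an unloader brace", but "At Centre 2 (Japan), patients will wear an off-loading brace and commence weight bearing immediately post-operatively". The Visit 1 section repeats the difference. Recording has a common end (Brace wear and documentation): "The final iButton will be obtained at Visit 2", which is the 6-month visit. The same section says "All patients will be provided with a hard copy bracing diary for the 6-month study duration" and, of the sensors, "all participants will therefore undergo five iButton swaps".

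**The concern.** A raw total reflects both how faithfully a patient wore the brace and how long the patient was allowed to wear it. The second part is fixed by centre. Within the brace arm, centre also fixes the early regimen: weight bearing in the brace from the start, or 8 weeks without weight bearing before the brace is applied. That regimen could itself affect the repair tissue. If outcomes differ between centres for this or any other reason, an unadjusted correlation attributes part of the difference to wear. Depending on the direction of the difference, it can create a wear effect or mask one. These correlations are the only wear-response analysis in the documents, and readers will tend to treat them as dose-response evidence.

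**Working it through.** **Inputs from the documents.** Brace start is week 0 (Centre 2) or week 8 (Centre 1). Recording ends at Visit 2, 6 months, taken as 26 weeks. Each centre randomises 10 patients to the brace. A sensor stores 1 month of data.

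**Possible wear.** Centre 2: 26 × 7 = 182 days. Centre 1: (26 − 8) × 7 = 126 days. The gap is 56 days, so Centre 1 has 56/182 = 31% fewer.

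**The plan's own figure.** Swaps = (months of recording, rounded up) − 1. A 6-month record needs 6 sensor periods, hence 5 swaps, which reproduces the protocol's number. A Centre 1 period of 18 weeks is 18/52 × 12 = 4.15 months, hence 5 − 1 = 4 swaps (3 if counted as 4 months). Five swaps for everyone therefore fits a 6-month record but not one that starts at week 8.

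**Assumptions.** The documents give no spread for wear and no centre difference in outcome, so both are varied. Total days = adherence × 126 or 182. Adherence is normal, clipped to 0–1, with the same distribution at both centres. Outcome has SD 1, is shifted by D at one centre, and has no relation to wear within either centre.

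**Approximation by hand** (70% adherence, SD 15 points, D = 1):
- Half the between-centre gap in mean wear: 0.70 × 56 / 2 = 19.6 days.
- Within-centre variance of wear: 0.15² × (126² + 182²)/2 = 0.0225 × 24,500 = 551.
- Correlation of centre with total days: 19.6 / √(19.6² + 551) = 19.6 / 30.6 = 0.64.
- Spurious wear–outcome correlation: 0.64 × 0.5 / √(0.5² + 1) = 0.29.

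**Simulation** (40,000 replicates, 10 + 10 patients, Pearson correlation on 18 df). The same case gives 0.66 and 0.30. The last three columns are false-positive rates at .05:

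| Exposure and assumed adherence | r, centre with wear | D = 0.5 | D = 1.0 | D = 1.5 |
|---|---|---|---|---|
| Days, 70%, SD 15 | 0.66 | 10% | 25% | 44% |
| Days, 70%, SD 25 | 0.49 | 8% | 15% | 25% |
| Days, 60%, SD 30 | 0.37 | 7% | 11% | 16% |
| Minutes: 70%, SD 15, minutes per day CV 40% | 0.38 | 7% | 11% | 16% |
| Minutes: 70%, SD 15, minutes per day CV 60% | 0.28 | 6% | 8% | 11% |

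A still tighter spread (days, 70%, SD 10) raises the first two rates to 13% and 36%. With D = 0 the rate is about 5% in every row: the unequal wear period does no harm unless outcomes also differ by centre. The centre-adjusted partial correlation (17 df) has mean spurious r of about zero and a false-positive rate of about 5% throughout.

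The SAP's .008 (0.05/6 = 0.0083) is stated for the group comparisons. Whether it governs the correlations is not said. At that threshold and D = 1, the unadjusted rate is about 13% for SD 10 and 2% for 60%/SD 30, against a nominal 0.8%.

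**The case against.** **Pooling is inferred.** The SAP does not say that both centres' wear data are analysed together, and the protocol names only Stanford facilities for the Visit 1 and Visit 2 scans. If one centre supplied all the wear data, the problem would not arise. This stands, so the point is conditional. But a two-centre protocol and a population defined only by arm lead naturally to a combined analysis, and if that is wrong the SAP should say so.

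**Five swaps and a 6-month diary for all suggest equal wear periods.** They do conflict with an 18-week period at Centre 1. They may instead mean that recording ran from Visit 1 at both centres, with no wear for the first 8 weeks at Centre 1, in which case possible wear still differs by 56 days. Nothing in the sensor section withdraws the stated difference in start.

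**The SAP already mitigates.** Change from baseline removes stable additive centre offsets, such as a constant measurement difference. It does not remove a regimen effect on recovery, and correlations with values at each time point are planned as well. Average minutes per day, if taken over days of wear, does not scale with the length of the period. Its denominator is undefined, however, and the correlations spelled out use totals.

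**Stronger readings.** A reader might infer that total wear is little more than a proxy for centre. Even at r = 0.66, centre accounts for under half the variance in total days (0.66² = 0.44), and for less under most other inputs, especially for minutes. A reader might also take 44% as the expected error rate, but that needs a 1.5 SD centre difference, which no document supports. Finally, a reader might conclude that cumulative wear must give way to the proportion of the period worn. Those are different questions (dose and adherence), and centre adjustment alone removes the bias.

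**Conclusion.** The concern holds, conditionally. If both centres contribute, the planned correlations mix wear with centre and with the early regimen. With 10 braced patients per centre and no true wear effect, centre correlates about 0.3 to 0.7 with total wear for an adherence SD of 15 points or more, and more strongly if adherence is tighter. Inflation ranges from negligible to several-fold. It depends on the assumed adherence spread, on whether days or minutes are used, and on a centre difference in outcome that the documents do not quantify.

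A reader might infer that the trial's superiority conclusion is compromised. The documents do not support that: these are brace-arm subgroup correlations, and the randomised comparison does not use them. The case for acting is that the correction is specific and almost free.

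**What to change.** 1. In the SAP, replace the unadjusted correlations with partial correlations or regressions that include centre. This costs about one degree of freedom among about 20 patients. Since the SAP reports its analyses in the past tense, this may mean rerunning them on existing data.
2. State which centres contribute wear data and which contribute MRI data. If only one does, say so, and the adjustment is not needed.
3. Optionally, as a sensitivity analysis, express wear relative to each patient's own wear period. The documents do not list start dates as a collected item, so take the start from the sensor or diary records, and define the denominator of average minutes per day.
4. Reconcile the five swaps and the 6-month diary for all participants with the week-8 brace start at Centre 1. This is a matter of documentation. This review takes no view on when bracing should begin.

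Separate centre estimates are not essential: with 10 patients, a correlation must exceed about 0.63 in size to differ from zero at .05, so they would say little.
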